	Appendix 1. Laboratory Parameters	40
	Appendix 2. ADAS-Cog (Alzheimer's Disease Assessment Scale-cognitive subscale)	41
	Appendix 3. MMSE (Mini-mental status examination).....	64
	Appendix 4. CDR-SOB (Clinical Dementia Rating-Sum of Box).....	70

Appendix 5. NPI (Neuropsychiatric Inventory).....	81
Appendix 6. GDS (Geriatric Depression Scale).....	94
Appendix 7. ADCS-ADL (Alzheimer's Disease Cooperative Study- Activities of Daily Living)....	95
Appendix 8. C-SSRS (Columbia-Suicide Severity Rating Scale)	104
Appendix 9. Instruction for Liposuction Procedure.....	114
Appendix 10. IP Administration Instruction for Clinical Sites.....	120

PROTOCOL SYNOPSIS

Name of Sponsor/Company: Nature Cell Co., Ltd. [name]	
Investigational Product: AstroStem	
Protocol Number	AST-ADP2-US01
Indication	Alzheimer's Disease (AD)
Protocol Title	A Phase 1/2, Randomized, Double-Blind, Placebo-Controlled Study to Evaluate the Safety and Efficacy of AstroStem, Autologous Adipose Tissue Derived Mesenchymal Stem Cells, in Patients with Alzheimer's Disease
Study Phase	Phase 1 and 2
Planned Number of Subjects	Total up to 22 subjects - Treatment group: AstroStem (2×10^8 cells/220 mL), N=11 - Control group: Saline 220 ml, N=11
Objectives	To evaluate the safety and efficacy of AstroStem (autologous adipose tissue derived mesenchymal stem cells, AdMSCs) in patients with Alzheimer's disease
Study Design	This is a randomized, double-blind, placebo-controlled, parallel-group comparison study in subjects with Alzheimer's Disease. Following first screening period, subjects will be randomly assigned into one of the following treatment arms: AstroStem and placebo. At Week -4, 30 mL of abdominal adipose tissue will be taken by liposuction from subjects. The adipose tissue samples will be sent to Biostar Stem Cell Research Institute to isolate AdMSCs. The isolated AdMSCs or saline will be sent to the clinical sites with identical syringes to preserve double-blinding of the study. A total 2×10^8 AdMSCs in 220 mL of saline or the same volume of saline will be administered via I.V. at Week 0. This procedure will be repeated 9 times at 2-week interval. Subjects will be scheduled for two follow-up visits at Weeks 30 and 52 to evaluate primary and secondary outcome endpoints.
Drug Administration	A total 2×10^8 AdMSCs in 220 mL of saline or the same volume of saline will be administered via I.V. for 2-6 hours to patients in the treatment group and the placebo group, respectively.
Study Visits	Visit 1 (Week -8) – Screening Visit 2 (Week -4) – Liposuction Visit 3 (Week 0) – 1 st injection of AstroStem or Placebo Visit 4 (Week 2) – 2 nd injection of AstroStem or Placebo Visit 5 (Week 4) – 3 rd injection of AstroStem or Placebo Visit 6 (Week 6) – 4 th injection of AstroStem or Placebo Visit 7 (Week 8) – 5 th injection of AstroStem or Placebo Visit 8 (Week 10) – 6 th injection of AstroStem or Placebo Visit 9 (Week 12) – 7 th injection of AstroStem or Placebo Visit 10 (Week 14) – 8 th injection of AstroStem or Placebo Visit 11 (Week 16) – 9 th injection of AstroStem or Placebo Visit 12 (Week 18) – 10 th injection of AstroStem or Placebo Visit 13 (Week 30) – 1 st follow-up Visit 14 (Week 52) – Final follow-up
Study Hypothesis	AstroStem treatment group has improvement on neurological/neurocognitive assessment from baseline at Week 30 compared to the placebo group.

Name of Sponsor/Company: Nature Cell Co., Ltd. [name]	
Investigational Product: AstroStem	
Protocol Number	AST-ADP2-US01
Indication	Alzheimer's Disease (AD)
Clinical Endpoints	
The primary endpoint used to determine the safety and efficacy of AstroStem is the following:
 
Number of subjects with treatment related adverse events as assessed by analysis of adverse events including symptoms, and abnormal findings on physical examination, vital signs, ECG, and standard laboratory examination resultsChange of ADAS-Cog (Alzheimer's Disease Assessment Scale-cognitive subscale) from baseline at Week 30 
The secondary endpoints used to determine the efficacy and safety of AstroStem are:
 
Change of MMSE (Mini-mental status examination) from baseline at Week 30Changes of CDR-SOB (Clinical Dementia Rating-Sum of Boxes) from baseline at Week 30Changes of NPI (Neuropsychiatric Inventory) from baseline at Week 30Changes of GDS (Geriatric Depression Scale) from baseline at Week 30Change of ADCS-ADL (Alzheimer's Disease Cooperative Study Activities of Daily Living) from baseline at Week 30Changes of C-SSRS (Columbia Suicide Severity Rating Scale) from baseline at Week 30Change of MRI imaging results from baseline at Week 30Biomarkers in blood: Amyloid beta 40, Amyloid beta 42, Amyloid precursor protein intracellular domain (AICD), soluble neuregulin-1 (sNRG-1)
Inclusion/Exclusion Criteria	
Inclusion Criteria
 
Male or female subjects aged 50 and above at the time of signing the Informed Consent formSubjects who can understand and provide written informed consent (assent)Subjects who have diagnosis of probable mild-to-moderate Alzheimer disease according to NINCDS-ADRDA (National Institute of Neurological and Communicative Disorders and Stroke; Alzheimer's Disease and Related Disorders Association) criteriaSubjects who have MMSE Score of 16 to 26 at screeningSubjects who are taking FDA-approved AD medications (donepezil, galantamine, memantine, rivastigmine or their combinations) treatment on a stable dosage for at least 3 months prior to screening.Subjects who have one (or more) identified adult caregiver (study partner) who is able to read, understand, and speak the designated language at the study site; either lives with the subject or sees the subject for ≥ 2 hours/day ≥ 4 days/week; and agrees to accompany the subject to each study visit and to participate in the subject's clinical assessments. 
Exclusion Criteria
 
Subjects who are females who are pregnant, nursing, or of childbearing potential while not practicing effective contraceptionSubjects who have signs of deliriumSubjects who have had cortical stroke within the preceding 2 yearsSubjects who have a prolonged QTc interval; >450 msec in male or >470 msec in female at screening

Name of Sponsor/Company: Nature Cell Co., Ltd. [name]	
Investigational Product: AstroStem	
Protocol Number	AST-ADP2-US01
Indication	Alzheimer's Disease (AD)
	
5. Subjects who have diagnosis of severe white matter hyperintensity (WMH), which is defined as \geq 25mm of the deep white matter and \geq 10mm of the periventricular capping/banding in lengths6. Subjects who have diagnosis of dementia or cause of cognitive impairment other than Alzheimer's disease7. Subjects who have a significant abnormal result in laboratory tests, in the opinion of the investigator8. Subjects who have participated in any investigational drug, stem cell therapy, or device trial within the previous 3 months at screening9. Subjects with any current psychiatric diagnosis other than AD if, in the judgment of the investigator, the psychiatric disorder or symptom is likely to confound interpretation of drug effect, affect cognitive assessments, or affect the subject's ability to complete the study10. Subjects who are known to have autosomal dominant mutation-associated presenile AD11. Subjects who show signs of AIDS (Acquired Immunodeficiency Syndrome), HBV (Hepatitis B Virus), HCV (Hepatitis C), VDRL (Venereal Disease Research Laboratory)12. Subjects who have any conditions that would contraindicate an MRI, such as the presence of metallic objects in the eyes, skin, or heart13. Subjects who have > 4 cerebral microhemorrhages (regardless of their anatomical location or diagnostic characterization as "possible" or "definite"), a single area of superficial siderosis, or evidence of a prior microhemorrhage as assessed by MRI14. Subjects who have history of malignant cancer within the last 5 years (The following is a partial list of conditions that are permissible for study entry: non-metastatic basal and/or squamous cell carcinoma of the skin, in situ cervical, or non-progressive prostate cancer)15. Subjects who have suspected active lung disease based on chest X-ray16. Subjects who are hypersensitive to fetal bovine serum or penicillin17. Subjects who are currently using immunosuppressants, cytotoxic drug, corticosteroids or similar steroid anti-inflammatory medication (e.g., Prednisone) on a regular basis (exceptions allowed include: regular use of steroid nasal sprays, topical steroids, and estrogen-replacement therapy)18. Subjects for whom the investigator judges the liposuction can cause any problems19. Subjects who have history of local anesthetic allergy
Statistical Analysis	The primary variable, score change of ADAS-Cog from baseline at Week 30 will be analyzed using T-test or Kruskal-Wallis test depending on the violation of normality assumption. The secondary efficacy variables include the percentage of subjects who show improvement along with several change scores from baseline. The percentage of subjects who show improvement will be compared between groups using chi-square test or Fisher's exact test. The change scores will be analyzed using T-test or Kruskal-Wallis tests, as appropriate. Safety variables will be summarized descriptively, by treatment group and visit. When the first 4 subjects complete Visit 4 at Week 2, one unblinded interim safety analysis of the subjects can be performed by an independent safety monitor to evaluate the safety of AstroStem without the suspension of subject enrollment. Change of vital signs and AEs will be evaluated.

SCHEDULE OF ASSESSMENTS

Procedure	Screen		Treatment										Follow-up		Early Termination
	V1	V2	V3	V4	V5	V6	V7	V8	V9	V10	V11	V12	V13	V14	
Tested Group	-W8	-W4	W0	W2	W4	W6	W8	W10	W12	W14	W16	W18	W30	W52	
Informed Consent ¹	V														
Inclusion/Exclusion Criteria	V														
Demographic information	V														
Medical/medication history	V														
Physical examination	V		V			V			V			V	V	V	V
Vital signs	V	V	V	V	V	V	V	V	V	V	V	V	V	V	V
Hematology, serum chemistry, and urinalysis ²	V		V			V			V			V	V	V	V
Pregnancy test ³	V		V									V	V	V	V
Electrocardiogram	V		V		V			V			V	V	V	V	V
Chest X-ray	V														
Liposuction		V													
Serum for IP		V	V	V		V		V							
ADAS-Cog			V		V			V			V	V	V	V	V
MMSE	V		V		V			V			V	V	V	V	V
CDR-SOB			V		V			V			V	V	V	V	V
NPI			V		V			V			V	V	V	V	V
GDS			V		V			V			V	V	V	V	V
C-SSRS			V		V			V			V	V	V	V	V
ADCS-ADL			V		V			V			V	V	V	V	V
MRI Scan	V							V				V	V	V	V
Biomarker ⁴			V									V	V	V	V
Drug administration			V	V	V	V	V	V	V	V	V	V			
Concomitant medications	V	V	V	V	V	V	V	V	V	V	V	V	V	V	V
Adverse events	V	V	V	V	V	V	V	V	V	V	V	V	V	V	V

¹ Informed Consent Form should be signed prior to any clinical trial related activities

² See Appendix 1 for the complete list of laboratory tests

³ Serum pregnancy test is performed for all females of childbearing potential.

⁴ Amyloid beta 40, Amyloid beta 42, Amyloid precursor protein intracellular domain (AICD), soluble neuregulin-1 (sNRG-1)

GLOSSARY AND ABBREVIATIONS

A β	Amyloid beta
AD	Alzheimer's Disease
ADAS-Cog	Alzheimer's Disease Assessment Scale-cognitive subscale
ADCS-ADL	Alzheimer's Disease Cooperative Study Activities of Daily Living
AdMSC	Adipose Tissue Derived Mesenchymal Stem Cell
AE	Adverse Event
AICD	Amyloid precursor protein Intracellular Domain
AIDS	Acquired Immunodeficiency Syndrome
ALT (SGPT)	Alanine Aminotransferase (Serum Glutamic Pyruvic Transaminase)
APP	Amyloid Precursor Protein
AST (SGOT)	Aspartate Aminotransferase (Serum Glutamic Oxaloacetic Transaminase)
BUN	Blood Urea Nitrogen
CDR-SOB	Clinical Dementia Rating-Sum of Boxes
CFR	Code of Federal Regulations
C-SSRS	Columbia Suicide Severity Rating Scale
CREDOS	Clinical Research Center for Dementia of South Korea
ECG	Electrocardiography
eCRF	Electronic Case Report Form
GCP	Good Clinical Practice
GDNF	Glial cell-derived Neurotrophic Factor
GDS	Geriatric Depression Scale
hASCs	Human Adipose-derived Stem Cells
HBV	Hepatitis B Virus
HCV	Hepatitis C Virus
ICH	International Conference of Harmonization
IRB	Institutional Review Board
ITT	Intent-to-Treat
MCH	Mean Corpuscular Hemoglobin
MCHC	Mean Corpuscular Hemoglobin Concentration
MCV	Mean Corpuscular Volume
MMSE	Mini-mental status examination
NINCDS-ADRDA	National Institute of Neurological and Communicative Disorders and Stroke; Alzheimer's Disease and Related Disorders Association
NPI	Neuropsychiatric Inventory
NT3	Neurotrophin 3
PP	Per Protocol
PT-INR	Prothrombin Time - International Normalized Ratio
RBC	Red Blood Cell Count
SAE	Serious Adverse Event
SD	Standard Deviation
sNRG-1	Soluble Neuregulin-1
VDRL	Venereal Disease Research Laboratory
VEGF	Vascular Endothelial Growth Factor
WBC	White Blood Cell Count
WMH	White Matter Hyperintensity

1. PURPOSE OF STUDY

The purpose of this study is to evaluate the safety and efficacy of AstroStem (autologous adipose tissue derived mesenchymal stem cells, AdMSCs) in patients with Alzheimer's disease.

2. INTRODUCTION

Alzheimer's Disease (AD) is the most prevalent neurodegenerative disorder in The United States affecting approximately 5.4 million Americans [1]. AD is characterized by progressive loss in memory and as well as a decline in the ability to learn that is associated with neuronal death. Well known hallmarks of AD are neuritic plaques and neurofibrillary tangles [2, 3] and extensive inflammation [4]. Currently, no treatment has been developed to fully cure or prevent the progression of dementia that is associated with AD.

In addition to neuritic plaques and neurofibrillary tangles, oxidative stress, mitochondrial dysfunction, hormone dysregulation, inflammation, mitotic dysfunction, calcium imbalance, and genetic risk factors are all involved in AD processes [5]. The disease is now recognized as multifactorial and consequently strongly demands more effective treatments.

Therapeutic potentials of stem cells in several brain disorders are enticing researchers to apply stem cell based therapies [6–9]. Among stem cells, adipose tissue-derived mesenchymal stem cells (AMSCs), mesenchymal stem cells isolated from adipose tissue, are well known for their pluripotency and ability to differentiate into mesenchymal and non-mesenchymal lineages [10]. AMSCs are readily accessible and show high proliferation rates in vitro with lower senescence ratios than bone marrow derived mesenchymal stem cells [11]. Considering clinical applications, AMSCs are the most suitable source of stem cells due to the possibility of intravenous transplantation of autologous AMSCs with no immune rejections, ethical problems or tumorigenesis [12] and intravenous injection is the most convenient, simple and safest method of administration.

The paracrine effects of stem cells, including the production of growth factors and anti-inflammatory cytokines and anti-apoptotic regulation, are strongly exerted and induce neural regeneration, remyelination and immunomodulation [13]. In a preclinical study, we demonstrated that intravenously injected stem cells could enter the brain through blood brain barrier and hASCs could have beneficial effects in a murine model of Alzheimer's disease [14]. Compared to placebo group, memory impairments, the number of amyloid plaques, protein level of Amyloid beta (A β) and Amyloid Precursor Protein (APP) were reduced after intravenous injection of hASCs in Tg2576 mouse brain. Furthermore, analysis of Tg2576 mouse brain revealed that anti-inflammatory cytokine, IL-10 and neurotrophic factors including vascular endothelial growth factor (VEGF), Glial cell-derived neurotrophic factor (GDNF), and Neurotrophin 3 (NT3) were significantly increased after the injection of hASCs. These findings suggest that a convenient and safe intravenous injection of hASCs might be very useful for the treatment of AD.

The clinical study of AstroStem aims to evaluate the safety and efficacy of AstroStem as a potential treatment for AD. Based on the preclinical results, AstroStem could be an effective treatment option with a mechanism of action that has not been explored for AD indication.

3. INVESTIGATIONAL PLAN

3.1 Study Design

This is a randomized, double-blind, placebo-controlled study to evaluate the efficacy and safety of AstroStem for the treatment of Alzheimer's Disease. Three investigational centers in the United States may be utilized so that a total of approximately 22 subjects will be randomized.

3.2 Selection of Study Population

The study population will be males or females, aged 50 and above, who have who have diagnosis of probable Alzheimer disease according to NINCDS-ADRDA (National Institute of Neurological and Communicative Disorders and Stroke; Alzheimer's Disease and Related Disorders Association) criteria with 16-26 MMSE score.

3.2.1 Inclusion Criteria

- 1) Subjects who are males or females of any race, aged 50 and above at the time of signing the Informed Consent Form
- 2) Subjects who can understand and provide written informed consent (assent).
- 3) Subjects who have diagnosis of probable mild-to-moderate Alzheimer disease according to NINCDS-ADRDA (National Institute of Neurological and Communicative Disorders and Stroke; Alzheimer's Disease and Related Disorders Association) criteria
- 4) Subjects who have MMSE Score of 16 to 26
- 5) Subjects who are taking FDA-approved AD medications (donepezil, galantamine, memantine, rivastigmine or their combinations) treatment on a stable dosage for at least 3 months prior to screening.
- 6) Subjects who have one (or more) identified adult caregiver (study partner) who is able to read, understand, and speak the designated language at the study site; either lives with the subject or sees the subject for ≥ 2 hours/day ≥ 4 days/week; and agrees to accompany the subject to each study visit and to participate in the subject's clinical assessments.

3.2.2 Exclusion Criteria

- 1) Subjects who are female who are pregnant, nursing, or childbearing potential while not practicing effective contraception
- 2) Subjects who have signs of delirium
- 3) Subjects who have had cortical stroke within the preceding 2 years
- 4) Subjects who have a prolonged QTc interval; >450 msec in male or >470 msec in female at screening
- 5) Subjects who have diagnosis of severe white matter hyperintensity (WMH), which is defined as $\geq 25\text{mm}$ of the deep white matter and $\geq 10\text{mm}$ of the periventricular capping/banding in lengths
- 6) Subjects who have diagnosis of dementia or cause of cognitive impairment other than Alzheimer's disease
- 7) Subjects who have a significant abnormal result in laboratory tests, in the opinion of the investigator
- 8) Subjects who have participated in any investigational drug, stem cell therapy, or device trial within the previous 3 months at screening
- 9) Subjects with any current psychiatric diagnosis other than AD if, in the judgment of the investigator, the psychiatric disorder or symptom is likely to confound interpretation of drug effect, affect cognitive assessments, or affect the subject's ability to complete the study
- 10) Subjects who are known to have autosomal dominant mutation-associated presenile AD
- 11) Subjects who show signs of AIDS (Acquired Immunodeficiency Syndrome), HBV (Hepatitis B Virus), HCV (Hepatitis C), VDRL (Venereal Disease Research Laboratory)
- 12) Subjects who have any conditions that would contraindicate an MRI, such as the presence of metallic objects in the eyes, skin, or heart
- 13) Subjects who have > 4 cerebral microhemorrhages (regardless of their anatomical location or diagnostic characterization as "possible" or "definite"), a single area of superficial siderosis, or evidence of a prior microhemorrhage as assessed by MRI

- 14) Subjects who have history of malignant cancer within the last 5 years (The following is a partial list of conditions that are permissible for study entry: non-metastatic basal and/or squamous cell carcinoma of the skin, in situ cervical, or non-progressive prostate cancer)
- 15) Subjects who have suspected active lung disease based on chest X-ray
- 16) Subjects who are hypersensitive to fetal bovine serum or penicillin
- 17) Subjects who are currently using immunosuppressants, cytotoxic drug, corticosteroids or similar steroid anti-inflammatory medication (e.g., Prednisone) on a regular basis (exceptions allowed include; regular use of steroid nasal sprays, topical steroids, and estrogen-replacement therapy)
- 18) Subjects for whom the investigator judges the liposuction can cause any problems
- 19) Subjects who have history of local anesthetic allergy

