4.1.1 Visit 1: Screening (Week -8)

The following screening assessments/procedures must be performed and the results documented within 2 weeks before Visit 2 unless otherwise indicated:

- Administer informed consent
- Review the inclusion and exclusion criteria (See Section 3.2)
- Record demographic data (i.e., date of birth, race and height).
- Record medical and medication history.
- Measure vital signs (sitting blood pressure, pulse, breathing, and temperature) and weight.
- Perform a complete physical examination.
- Measure 12-lead ECG.
- Collect blood and urine samples for hematology, serum chemistry, pregnancy test (only for women of childbearing potential) and urinalysis.
- Complete MMSE assessment
- Perform chest X-ray.
- Perform MRI scan including fluid-attenuation inversion recovery (FLAIR) and T2*-weighted gradient-recalled-echo (GRE) sequences.

[figure not shown]

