4.1.2 Visit 2 (Week -4)

Visit 2 will occur approximately 4 weeks (\pm 1 week) after Visit 1. During this visit, the following assessments/procedures should be performed:

- Confirm eligibility and perform randomization instructed in Section 3.5.6.
- Measure vital signs (sitting blood pressure, pulse, breathing, and temperature) and weight.
- Record any changes in concomitant medications.
- Record any adverse events, if applicable.
- In sterile conditions, collect blood and harvest approximately 30 mL of fat using the syringe liposuction technique with Tumescent (or super-wet) local anesthesia (Please see the detail procedures in Appendix 9).
- Ship the packaging box containing the harvested syringes and serum tubes to the lab designated by the sponsor (pre-labeled).

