7.4 Procedures for Managing Microhemorrhages and Cerebral Vasogenic Edema

MRI scan will be performed at screening, Visit 9 (Week 12), Visit 13 (Week 30), Visit 14 (Week 52), and/or Early Termination Visit. The protocols for MRI scans should include fluid-attenuation inversion recovery (FLAIR) and T2-weighted gradient-recalled-echo (GRE) sequences. Standards for the detection of cerebral microhemorrhage or superficial siderosis will include: 2D T2 GRE; field strength of 1.5 Tesla or greater; slice thickness of 5mm or less; Echo Time (TE) of 20 ms or greater. Standard FLAIR sequences are generally appropriate for the detection of cerebral vasogenic edema.

Subjects who are found to have new clinically asymptomatic microhemorrhages will be followed up closely, and a follow-up MRI will be done to evaluate the stability of those lesions.

All Principal Investigators will be notified of the possible occurrence of cerebral vasogenic edema, its imaging manifestations, and the clinical signs and symptoms that may accompany this phenomenon. They will also be told of the measures to be taken if cerebral vasogenic edema occurs. Those measures will include more frequent serial MRI scans until the imaging abnormalities resolve, and consideration of treatment with high-dose dexamethasone if symptoms are severe.

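### Exclusion criterion 13 holds two microhemorrhage limits, more than 4 and any prior one, that cannot both be the intended limit

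*Protocol*

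**What the plan says.** Criterion 13 in Protocol 3.2.2 opens with a count: "Subjects who have > 4 cerebral microhemorrhages". A parenthesis attached to that count says that it applies "regardless of their anatomical location or diagnostic characterization as" possible or definite. The sentence then adds two further grounds: "a single area of superficial siderosis, or evidence of a prior microhemorrhage as assessed by MRI". The Synopsis has the same criterion, ending in "evidence of a prior microhemorrhage as assessed by MRI", so the second location does not resolve the first.

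The criteria are reviewed at Visit 1 (Protocol 4.1.1). At Visit 2 the site must "Confirm eligibility and perform randomization instructed in Section 3.5.6" (Protocol 4.1.2). On sites, Protocol 3.1 says: "Three investigational centers in the United States may be utilized so that a total of approximately 22 subjects will be randomized".

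Protocol 7.4 has a sentence beginning "Standards for the detection of cerebral microhemorrhage or superficial siderosis will include". What follows is scanner settings, and then follow-up of new lesions found on study. It gives no entry count and does not define possible, definite or prior.

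**The concern.** A limit of more than 4 implies that 1 to 4 lesions are tolerated. A ground that is met by one prior lesion implies that none is. If zero was meant, the number 4 and its careful qualifier have no work to do for definite lesions. If four was meant, the last ground excludes people whom the sponsor wanted to admit. Either way, one part of the sentence does not express the intended rule.

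This is a brain-safety entry rule, applied before randomization at up to three sites. A site working from the count and a site working from the last ground would decide differently on a subject with 1 to 4 lesions.

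The choice also decides what counts as an eligibility violation. SAP 4.6.2 puts breaches of the entry criteria among the significant protocol violations to be listed. Protocol 3.3 requires withdrawal for a violation that the sponsor or investigator judges significant.

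**Working it through.** The plan states no figure to reproduce here. The check applies the sentence's logic to each kind of MRI finding, with siderosis set aside.

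**Inputs** (Protocol 3.2.2, item 13)

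- First ground: met when definite plus possible lesions total 5 or more.
- Last ground: met by 1 or more lesions. No rating is given, so there are two readings. Reading A: a lesion of any rating is evidence. Reading B: only a definite lesion is evidence. Both take 'prior' to include a lesion already visible on the screening MRI.
- Rule: exclude if the first ground OR the last ground is met.

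| Finding on MRI | First ground | Last ground, A | Last ground, B | Text as written, A | Text as written, B |
|---|---|---|---|---|---|
| No lesion | no | no | no | not excluded | not excluded |
| 1 to 4, at least one definite | no | yes | yes | excluded | excluded |
| 1 to 4, all possible | no | yes | no | excluded | not excluded |
| 5 or more, at least one definite | yes | yes | yes | excluded | excluded |
| 5 or more, all possible | yes | yes | no | excluded | excluded |

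**What follows**

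- Once any definite lesion is present, the last ground is met on both readings and the subject is excluded. The count of 4 is redundant for definite lesions.
- Under A the count never decides the result. Under B it decides only the bottom row.
- The text does not settle the third row, because the possible/definite qualifier belongs to the first ground only.
- Taken as stand-alone rules, the two limits disagree under A for every total from 1 to 4. Under B they disagree for 1 to 4 lesions with at least one definite, and also for 5 or more lesions all rated possible: a limit of 0 counting only definite lesions would admit that subject, and the count of 4 would not. This matters for the amendment.
- A third reading takes 'prior' to mean a lesion on an earlier scan. The count would then govern the screening MRI, and 1 to 4 lesions on it would not exclude unless an earlier scan had shown one. The text does not say this, and a lesion already present at screening is naturally prior, but the reading is not ruled out.

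**Other places that might settle it.** Protocol 4.1.1 and 4.1.2 point back to the criteria. Protocol 7.4 covers scan settings and new lesions. The SAP does not mention the limit.

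**The case against.** The best reply is that a list joined by 'or' cannot contradict itself. Meeting one ground never conflicts with another, and nothing in the sentence declares 1 to 4 lesions acceptable. The natural result is clear for definite lesions and errs toward exclusion. Harm would require a site to overlook the last ground. The consequences are also limited: SAP 4.6.2 produces a listing, and withdrawal under Protocol 3.3 depends on a judgement of significance.

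Most of this stands. The grounds are redundant, not logically incompatible. A reader might infer that the criterion cannot be applied at all; the 'or' shows that it can, with the stricter ground governing. A reader might also infer that excluding lesions rated only possible is the literal rule; the text does not settle that.

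The reply does not show which limit was meant, what to do with 1 to 4 possible lesions, or whether 'prior' points to an earlier scan. A safety rule with a detailed count that does no work for definite lesions still invites different handling by different sites.

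**Conclusion.** The point holds as a wording defect in a stated safety rule, and it should be fixed. The statement that one definite lesion excludes rests on 'prior' covering a lesion seen on the screening MRI.

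The size cannot be given in subjects, because the documents report neither the number screened nor the prevalence of microhemorrhages. The exposure is confined to subjects with 1 to 4 lesions, unless the count is deleted without a rule on possible lesions; the last row of the table then opens too.

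A reader might infer that ineligible subjects were enrolled. SAP 4.9 reports an interim look at the first 4 subjects, so subjects had entered by then, but nothing shows that any of them had a microhemorrhage or that any site misapplied the criterion.

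A reader might also infer that the efficacy results are affected. No population, test or estimate in the SAP refers to this criterion, and SAP 4.7 bases all efficacy analyses on an ITT population whose definition does not depend on eligibility. No statistical result changes.

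**What to change.** Amend criterion 13 in Protocol 3.2.2 and in the Synopsis to one threshold, set by the sponsor's medical team:

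- **Either** exclude any microhemorrhage on the screening MRI and state that lesions rated possible count. That statement keeps 5 or more possible lesions excluded once the count is removed.
- **Or** keep the limit of more than 4 with its qualifier, and correct or delete the last ground.

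Until the amendment is in force, tell sites to exclude anyone with 1 or more lesions, possible ones included. Present this as a conservative interim rule and not as what the text says.

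Check the existing screening MRI reports of enrolled subjects for definite lesions only, since those breach the last ground as written. Subjects with only possible lesions should not be labelled violators of a rule that the protocol does not clearly contain. Record how any subject found is handled under Protocol 3.3.

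The cost is one medical decision, one sentence in two places, a site memo, and a review of reports for at most about 22 subjects. No new scans are needed. The protocol does not require reports to record counts or ratings, so some existing images may need a second read.
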